5 STUDY SCOPE AND DURATION

This is a multicenter, prospective, non-randomized, single arm, open-label early feasibility study. Six (6) subjects with biopsy confirmed localized pancreatic cancer (AJCC clinical stage IA-III) having completed a course of induction chemotherapy and indicated for image-guided radiotherapy will be recruited for this study and followed for a minimum of 6 months after injection of the TraceIT hydrogel. **This visit serves as the end of the study for assessing device safety.** Subjects will also be required to return for long-term follow-up for up to 18 months.

Prior to enrollment, potential study candidates will undergo a thorough physical examination and documentation of medical/surgical history. A baseline Computed tomography (CT) simulation will be performed by Radiation Oncology department to generate a baseline RT plan. Subjects meeting the study eligibility criteria will undergo transduodenal injection of TraceIT Tissue Spacer under endoscopic ultrasound guidance performed by a participating endoscopist experienced with similar procedures. As part of the subjects' standard of care, a CT simulation scan will be acquired post TraceIT Tissue Spacer injection. A second radiation treatment plan will be generated using this CT simulation scan and the subject will begin RT for pancreatic cancer according to this post-injection plan. During the last fraction of RT, acute duodenal toxicity will be scored using CTCAE v4.0 criteria.

Following the course of RT, subjects will be required to return for follow-up evaluations 2-6 weeks after radiation therapy for a resectability assessment, followed by visits at 3, 6, 12 and 18 months.

The Sponsor will utilize a Clinical Events Committee (comprised of physicians experienced in treating pancreatic cancer) to provide ongoing review and adjudication of adverse events at an individual and aggregate level and to monitor emerging data with respect to device effectiveness. Any serious and/or unanticipated adverse events will be submitted for committee review within 48 hours of the Sponsor's receipt of notification of such events so that an evaluation of the risk/benefit assessment of the investigational treatment can be performed.

The study will be conducted at up to **4** investigational sites in the United States. Enrollment is anticipated to take approximately 3 months. Duration of participation for subjects is approximately 22 months.

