Unresectable²	
Distant metastasis (including non-regional lymph node metastasis)
 
Head/uncinate process:
 
 Solid tumor contact with SMA $>180^\circ$. Solid tumor contact with the CA $>180^\circ$. Solid tumor contact with the first jejunal SMA branch 
Body and tail
 
 Solid tumor contact of $>180^\circ$ with the SMA or CA. Solid tumor contact with the CA and aortic involvement 	
Head/uncinate process:
 
 Unreconstructible SMV/PV due to tumor involvement or occlusion (can be due to tumor or bland thrombus). Contact with most proximal draining jejunal branch into SMV 
Body and tail
 
 Unreconstructible SMV/PV due to tumor involvement or occlusion (can be due to tumor or bland thrombus)

¹Al-Haraybi MM, Jarnagin RR, Merchant ST, et al: Pancreatic ductal adenocarcinoma: radiology reporting template: consensus statement of the Society of Abdominal Radiology and the American Roentgen Ray Society. Radiology 2011; 259:248-260.

²Solid tumor contact may be replaced with increased haziness/stranding of the fat surrounding the peri-pancreatic vessels (typically seen following neoadjuvant therapy); this finding should be reported on the staging and follow-up scans. Decision on resectability status should be made in these patients, in consensus at multidisciplinary meetings/discussions.

Note: All recommendations are category 2A unless otherwise indicated.

Clinical Trials: NCCN believes that the best management of any patient with cancer is in a clinical trial. Participation in clinical trials is especially encouraged.

Version 2.2017, 04/27/17 © National Comprehensive Cancer Network, Inc. 2017. All rights reserved. The NCCN Guidelines[®] and this illustration may not be reproduced in any form without the express written permission of NCCN.

PANC-B

3. Tumor is clearly delineable from duodenum and no clear evidence of invasion of the duodenum is seen at time of EUS performed for either diagnosis or fiducial placement.
4. Subject is able to comply with motion management guidelines.
5. Radiotherapy or chemoradiotherapy for treatment of the disease is indicated.
6. In Investigator's opinion, medically fit to undergo endoscopy for fiducial marker implantation and TraceIT administration.
7. Subjects Screening/Baseline laboratory testing must meet the following laboratory value criteria:

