6.5 Subject Withdrawal

For any subject who withdraws their consent following enrollment, the reason(s) for withdrawal will be documented on the appropriate CRF. In the event that a study subject does not finish their course of RT, the subject should be followed through 6 months from the date of the TraceIT hydrogel injection, whichever occurs sooner. For these subjects, participation will be concluded at that time and the subject will not participate in the longer-term toxicity assessment phase. Every attempt will be made to contact subjects who are non-compliant or lost to follow-up, and such attempts will be documented in the subject's study record.

Subjects may be replaced at the discretion of the Sponsor.

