7.2 General

The statistical analysis of the data obtained from this study will be performed using SAS[®] Version 9.3 or higher.

All data collected in this study will be documented using summary tables and subject data listings. Continuous variables will be summarized using descriptive statistics, specifically the mean, median, standard deviation, minimum and maximum. Categorical variables will be summarized by frequencies and percentages.

Changes from baseline in dosimetric parameters and quality of life parameters will be assessed using a paired t-test or, if not normally distributed, the nonparametric Wilcoxon Signed-Rank test for continuous variables and Chi-Square and/or McNemar's test for dichotomous variables. Nominal p-values associated with statistical tests will be reported, but no significance level will be assigned to the values. No adjustments to nominal p-values are planned since this is a hypothesis-generating study.

A detailed statistical analysis plan will be developed and finalized prior to database lock.

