7.6.5 Other Outcome Measures

All other measures as identified in Section 6.1.3 not described above will be evaluated in accordance with the general statistical methods previously identified. The following definitions will be used for PFS and OS:

- Progression-Free Survival (PFS): defined as the interval between the start of induction chemotherapy (prior to RT) to treatment failure (local, regional or distant progression) or death (in months).
- Overall Survival (OS): defined as the interval between the start of induction chemotherapy (prior to RT) to death (in months).

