1 PROTOCOL SUMMARY

TraceIT Tissue Spacer consists of a pre-filled glass syringe containing the absorbable radiopaque cross-linked polyethylene glycol (PEG) hydrogel spacer and a delivery mechanism (syringe and needle) packaged in a single use kit. TraceIT Tissue Spacer is a radiopaque hydrogel material intended to temporarily position the duodenum away from the pancreas in subjects undergoing Radiation Therapy (RT) for treatment of pancreatic cancer and in creating this space. It is the intent of TraceIT Tissue Spacer to reduce the radiation dose delivered to the duodenum during radiotherapy. When used as a spacer, the TraceIT hydrogel radiographically marks the area for radiotherapy planning and localization.

The TIPS Pilot Study is a multicenter prospective, single-arm early feasibility study, with up to 18-month follow-up. The objective is to evaluate the feasibility, radiotherapy benefits, and safety when using TraceIT Tissue Spacer to create space between the pancreas and duodenum. The study will be conducted at up to four (4) investigational sites in the United States to enroll six (6) subjects with localized (resectable, borderline resectable, or locally advanced) pancreatic cancer (defined per NCCN guidelines) having completed induction chemotherapy if required and for whom a course of radiotherapy (RT) is indicated.

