3 ENDPOINT ANALYSIS

All data collected in this study will be documented using summary tables and subject data listings. Continuous variables will be summarized using descriptive statistics, specifically the mean, median, standard deviation, minimum and maximum, when appropriate.

Categorical variables will be summarized by frequencies and percentages.

Changes from baseline in dosimetric parameters and quality of life parameters will be assessed using a paired t-test or, if not normally distributed, the nonparametric Wilcoxon Signed-Rank test for continuous variables and Chi-Square and/or McNemar's test for dichotomous variables.

Nominal p-values associated with statistical tests will be reported, but no significance level will be applied to the values. No adjustments to nominal p-values are planned since this is a hypothesis-generating study.

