The following definitions will be used for Progression-Free Survival (PFS) and Overall Survival (OS) analysis:

- Progression-Free Survival (PFS): defined as the interval between the start of induction chemotherapy (prior to RT) to the earliest treatment failure (local, regional or distant progression) onset date or death (in months). Treatment failure events will be reported as SAE and adjudicated by CEC.
- Overall Survival (OS): defined as the interval between the start of induction chemotherapy (prior to RT) to death (in months).

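### PFS and OS run from the start of induction chemotherapy, which an eligible subject may not have had, and no rule covers a subject still event-free when follow-up ends

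*SAP*

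**What the plan says.** **Origin.** SAP 3.3.1 has "Overall Survival (OS): defined as the interval between the start of induction chemotherapy (prior to RT) to death (in months"; PFS has the same start and ends at the earliest progression or death. Protocol 7.6.5 uses the same origin. Neither document offers another.

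**Who is enrolled.** SAP 1 describes subjects "having completed induction chemotherapy if required", and the Study Design row of Protocol 2 has the same qualifier. Protocol 5 omits it and describes subjects "having completed a course of induction chemotherapy and indicated for image-guided radiotherapy will be recruited for this study". None of the criteria in Protocol 6.3.1 and 6.3.2 mentions induction; the nearest, criterion 5, reads "Radiotherapy or chemoradiotherapy for treatment of the disease is indicated".

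**Method.** Protocol 7.6.5 says: "All other measures as identified in Section 6.1.3 not described above will be evaluated in accordance with the general statistical methods previously identified". In Protocol 7.2 those methods are: "Continuous variables will be summarized using descriptive statistics, specifically the mean, median, standard deviation, minimum and maximum", with frequencies and percentages for categorical data. Protocol 7.8 rules out imputing missing data. SAP 3 adds: "All data collected in this study will be documented using summary tables and subject data listings". Neither document names a censoring rule, a last-contact rule or a time-to-event estimator. SAP 3.3 says only that survival is assessed through follow-up.

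**End of follow-up.** The last visit is 18 months after the index procedure (Protocol 6.4.15). If RT is not finished, "the subject should be followed through 6 months from the date of the TraceIT hydrogel injection" (Protocol 6.5). After withdrawal there is no required follow-up (Protocol 6.4.2).

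**The concern.** A time-to-event variable needs an origin that every subject has and a rule for subjects without the event. Here the stated origin can be absent in someone the plan allows in. The population includes resectable disease, and Protocol 4 describes pre-operative chemoradiotherapy for such patients, so this case is foreseeable.

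Where the origin does exist, it lies before enrolment. A subject had to survive from induction to the index procedure to be in the study, so that stretch is survival by selection. Its length varies between subjects, while follow-up is counted from the index procedure.

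At the other end, an interval to death does not exist for a subject alive at last contact, and the methods cited give no way to carry that subject into a mean or median. If the rules are left until the data are in, they will be chosen with six known outcomes in view.

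**Working it through.** The documents state no PFS or OS figure, event count or power, so there is nothing to reproduce. The check is first a reading of the definitions against the subjects the plan admits, then an illustration of how often the gaps would bite.

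**1. Applying the definition as written**

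| Subject | Start | End | PFS or OS value |
|---|---|---|---|
| Had induction, event observed | induction start | event | defined, includes time before enrolment |
| Had induction, event-free at last contact | induction start | none stated | undefined |
| No induction, with or without event | none stated | event or none | undefined |

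On the text of Protocol 5 alone, the last row is empty. On the text of SAP 1, Protocol 2 and the criteria in Protocol 6.3, it is not. The middle row arises on either text.

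**2. Missing origin.** The assumed share *p* of eligible subjects without induction is not in the documents. With six subjects, P(at least one) = 1 − (1 − *p*)^6:

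- *p* = 0.10: 1 − 0.90^6 = 0.469
- *p* = 0.20: 1 − 0.80^6 = 0.738
- *p* = 0.30: 1 − 0.70^6 = 0.882

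Each such subject removes 1/6 = 16.7% of a six-subject summary.

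**3. No event by 18 months.** Assume exponential times from the index procedure with median *m* months; *m* is not in the documents. Then S(18) = 2^(−18/*m*), and P(at least one of six event-free) = 1 − (1 − S)^6.

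| Endpoint | Assumed *m* | S(18) | Expected of 6 | P(at least one) |
|---|---|---|---|---|
| OS | 9 | 0.250 | 1.5 | 0.822 |
| OS | 12 | 0.354 | 2.1 | 0.927 |
| OS | 18 | 0.500 | 3.0 | 0.984 |
| OS | 24 | 0.595 | 3.6 | 0.996 |
| PFS | 6 | 0.125 | 0.75 | 0.551 |
| PFS | 9 | 0.250 | 1.5 | 0.822 |
| PFS | 12 | 0.354 | 2.1 | 0.927 |

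These take all six subjects to be in the MITT population, which SAP 4.1.2 makes primary for non-safety outcomes; a smaller MITT lowers the probabilities. Unfinished RT and withdrawal end follow-up sooner and raise them.

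**4. Unequal windows.** If the time from induction start to the index procedure is *a* months (assumed), the longest observable time is 18 + *a*: 20, 22 or 24 months for *a* = 2, 4 or 6.

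**5. PFS assessment dates.** The only scheduled restaging CT after RT is at 2-6 weeks (Protocol 6.4.11), and the month-6 MRI is there to look for TraceIT (Protocol 2, Study Design). Censoring PFS at the last visit or at the last disease assessment could therefore give very different times.

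**The case against.** PFS and OS are additional data (Protocol 6.1.3) and exploratory (SAP 3.3), with six subjects and no hypothesis. Listings of all collected data are planned, so no raw date is lost. Protocol 5, taken alone, leaves nobody without an origin. Protocol and SAP agree on induction start, and replacing it outright is partly a matter of preference. SAP 7.3 lets derivation rules be placed in code or footnotes, and event status at last follow-up could be shown as a count and percentage under Protocol 7.2.

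Most of this bears on weight, and that part stands. It does not close the gap. Protocol 5 conflicts with the protocol's own summary and with the SAP. SAP 7.3 says where rules will be recorded but supplies none for these endpoints. A count of events is not the interval that the plan defines.

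A reader might infer that OS will be understated by some number of months. The documents do not support that. It would require summarising observed deaths only, which neither document says will be done, and it would rest on assumed survival. An 18-month window could not recover the larger differences under any method.

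A reader might also count the non-injection subjects, followed for about 30 days (Protocol 6.4.7), as extra censoring. They are in ITT but not in MITT, so they do not raise the censoring share in the primary population for these outcomes.

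**Conclusion.** The point holds as a defect in a stated rule. On the SAP and protocol summaries, the definition fails for an eligible subject without induction. On any reading, it gives no interval to a subject alive or progression-free when follow-up ends. The first gap depends on which enrolment text governs; the second does not.

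The 47-88% chance of at least one missing origin rests on an assumed 10-30% share. The 82-99.6% (OS) and 55-93% (PFS) chances of at least one event-free subject at 18 months rest on assumed medians, exponential times and six subjects in MITT. They show that the gaps are likely to matter in practice and do not measure bias.

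A reader might conclude that starting at induction biases survival by a known amount. It does not: it is a different definition that mixes selected pre-enrolment time with follow-up and so limits interpretation. Feasibility and the defined safety endpoint are unaffected. The SAP's instruction to report treatment failures as SAEs, set against the SAE criteria in Protocol 9.1, is a separate matter.

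**What to change.** 1. Reconcile Protocol 5 with Protocol 2 and SAP 1 on whether every subject has completed induction.
2. In the SAP, report PFS and OS from the index procedure date. Every ITT and MITT subject has it, and SAP 3.4 and 5.1.5 already use it for AE and medication timing. Keep time from induction start for subjects who had induction.
3. In the planned listing, give each subject's time with event or censoring status. Censor OS at last contact and PFS at last disease assessment, and state which assessments count. Kaplan-Meier is optional with six subjects.

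**Cost.** A SAP amendment approved before the analyses (SAP 5.6). If the protocol definition is also changed, a protocol amendment with IRB approval, and FDA approval if the change is significant (Protocol 10.3). No extra procedures for subjects. Times from index will be shorter than times from induction for those who had it, so the two should be labelled clearly.

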3.4 Safety Endpoint

Any adverse event (AE) occurred Procedure through 18-month visit will be recorded and listed. All collected AEs will be recorded by body system and preferred term in accordance with NCI Common Terminology Criteria for Adverse Events (CTCAE) v4.0 (NCI, Oct 2009) for severity and/or MedDRA term.

The safety endpoint for this study is defined as “TraceIT administration procedure-related events which result in a delay in initiation of RT” as reviewed and adjudicated by a Clinical Events Committee.

The timing (month) of AE will be categorized as <=3 months, >3 to <=6 months, >6 to <=12 months, >12 to <=18 months, by its value calculated as:

(Date of AE started - Date of index procedure + 1) / (365.25/12) and rounded to 2 decimal places.

SADE is defined as a serious adverse event that is believed to have been caused by or is associated with the device. UADE is defined as any serious adverse effect on health or safety, or any life-threatening problem or death caused by, or associated with, a device if that effect, problem or death was not previously identified in nature, severity or degree of incidence in the Investigational Plan, or any other unanticipated serious problem associated with a device that relates to the rights, safety or welfare of subjects. SADEs and UADEs will be investigated immediately once occurred and if the sponsor determines that unreasonable risk to subjects is possible, the study will be terminated.

To standardize the reporting, a Clinical Events Committee (CEC) was convened at the beginning of the study to provide:

- Continuous review and validation of all adverse events that occur over the course of the study and the subsequent classification of these adverse events as related to the device or procedure.
- Oversight for issues affecting general subject welfare, including recommendations on changes to the protocol or device and if appropriate recommendation concerning early study termination if new information is learned that would affect the risk/benefit analysis presented within this clinical investigational plan.

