6.1.1 Safety Endpoints

Subjects will be monitored for adverse events and RT toxicity (using CTCAE v4) and in particular for the safety endpoint defined as “TraceIT administration procedure-related events which result in a delay in initiation of RT” as reviewed and adjudicated by a Clinical Events Committee.

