7.7 Safety Analysis

Incidence of adverse events will be summarized by body system and preferred term in accordance with NCI Common Terminology Criteria for Adverse Events (CTCAE) v4.0 (NCI, Oct 2009) for severity and/or MedDRA term. The incidence of adverse events will be summarized by term, by term and procedure/device relationship, and by term and severity. All adverse events occurring at the time of initiation of fiducial marker placement or attempted injection and up through and including the 18 month visit will be recorded and listed. In addition to the general presentation of safety events, the following will be calculated and reported:

- The number and percentage of subjects who experience TraceIT administration procedure-related events which result in a delay in initiation of RT.

- The number and percentage of subjects with at least one duodenal adverse event presented by grade and timing; i.e., acute (within 3 months) and late (>3months). A similar presentation will be provided for non-resected subjects only.

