8.2 Risks of Study Procedures and Investigational Material

The associated risks and potential benefits of the procedure and the device are provided below.

Risks associated with radiation therapy of the pancreas

The following risks are associated with radiation therapy of the pancreas:

- Pancreatitis
- Duodenal hemorrhage
- Duodenal stricture
- Duodenitis
- Bleeding
- Obstructive jaundice
- Diarrhea
- Nausea/vomiting
- Epigastric/abdominal pain
- Mucositis

Risks associated with transduodenal placement of fiducial markers:

- Bleeding
- Pain
- Pancreatitis
- Infection
- Nerve damage
- Anesthetic related complications
- Fiducial implant misplacement or migration
- Foreign body reaction
- Tumor seeding

Specific Potential Risks associated with the study treatments

Potential complications that may be associated with the use of TraceIT Tissue Spacer include, but are not limited to:

- Pain associated with TraceIT Tissue Spacer injection
- Pain or discomfort associated with TraceIT hydrogel
- Needle penetration of pancreas during injection
- Injection of TraceIT Tissue Spacer into pancreas, duodenal wall or other organs
- Local inflammatory reactions
- Infection
- IV injection of air/material
- Duodenal stricture
- Duodenal mucosal damage, ulcers or necrosis
- Bleeding
- Delay in initiation of RT or surgery

- Potential to exacerbate local progression due to protection of undiagnosed/microscopic duodenal invasion
- Potential for hydrogel migration

The TraceIT Tissue Spacer is completely synthetic and therefore allergic reactions are not anticipated.

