9.1.2 Clinical Events Committee

The Sponsor will utilize a Clinical Events Committee (CEC) to provide ongoing review and adjudication of adverse events and review of emerging device performance data. Members of the CEC will include physicians with a specialty in treating subjects with pancreatic cancer including a radiation oncologist and a gastroenterologist. The CEC will be charged with the following responsibilities:

- Continuous review and validation of all adverse events that occur over the course of the study and the subsequent classification of these adverse events as related to the device, procedure, radiotherapy or other.
- Provide oversight for issues affecting general subject welfare, including recommendations on changes to the protocol or device and if appropriate recommendation concerning early study

termination if new information is learned that would affect the risk/benefit analysis presented within this clinical investigational plan.

The Sponsor will meet with the CEC on a regular and ongoing basis. All serious and/or unanticipated adverse effects will be reviewed with the CEC within 48 hours of Sponsor receiving such notification.

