3.4.1 Statistical Methods

CEC adjudicated AEs will be summarized by term, by term and procedure/device relationship, and by terms and severity (CTCAE Grade). In addition to the general presentation of safety events, the following will be calculated and reported:

- The number and percentage of subjects who experienced TraceIT administration procedure-related events which result in a delay in initiation of RT
- The number and percentage of subjects with at least one duodenal adverse event presented by grade and timing; i.e., acute (within 3 months) and late (>3 months). A similar presentation will be provided for non-resected subjects only.

Additionally, the numbers and percentages will be calculated for subjects who have developed one or more following events: AEs, SAEs, UADE, SADE, procedure related

AEs, device related AEs, radiation therapy related AEs, duodenal related AEs by site and total.

Adverse event overall listing will include AE CTCAE term, AE CTCAE SOC, onset days since procedure and duration, AE attribution, CTCAE grade and adjudication term, SAE and classification, UADE, action taken, outcome and residual effects.

Single imputation will be implemented for partial start/end dates (missing month and/or day) of adverse events, or concomitant medications.

For the missing start date:

- Only the start day is missing: the 15th day of the month will be used if the resulted imputed date is after the index procedure date; otherwise the procedure date will be used.
- Both the start day and the start month are missing: the 15th day of January will be used if the resulted imputed date is after the index procedure date; otherwise the procedure date will be used.

For the missing end date:

- If the end day is missing, the 15th day of the month will be used if the resulted imputed date is after the corresponding start date; otherwise the last day of the month will be used.
- If end day and end month are both missing, the 15th day of December will be used if the resulted date is after the corresponding start date; otherwise the 31st day of December will be used.

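### The one defined safety endpoint counts RT delays from procedure-related events only, so a delay adjudicated as device-related alone would fall outside it

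*SAP*

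**What the plan says.** The endpoint has the same restriction wherever it is stated: the Protocol Summary, Protocol 6.1.1 and 7.7, and SAP 3.4 and 3.4.1.

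- **Definition.** Protocol 6.1.1 provides for general monitoring of adverse events and RT toxicity, and "in particular for the safety endpoint defined as" events of the kind SAP 3.4 words as "TraceIT administration procedure-related events which result in a delay in initiation of RT", adjudicated by the Clinical Events Committee (CEC). No other safety endpoint is defined.
- **Statistic.** Protocol 7.7 asks for "The number and percentage of subjects who experience TraceIT administration procedure-related events which result in a delay in initiation of RT". SAP 3.4.1 repeats this almost word for word.
- **Attribution.** Protocol 9.1.2 charges the CEC with review of all adverse events and "subsequent classification of these adverse events as related to the device, procedure, radiotherapy or other". SAP 3.4 names only device and procedure. SAP 3.4.1 counts subjects with procedure-related AEs and, as separate items, "device related AEs, radiation therapy related AEs, duodenal related AEs by site and total".
- **Known risks.** In Protocol 8.2, the complications that may follow use of TraceIT include "Duodenal mucosal damage, ulcers or necrosis" and "Delay in initiation of RT or surgery".

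**The concern.** The endpoint is limited by one attribution class, procedure, while the harm it is meant to detect (postponed cancer treatment) can also arise from the other class, the implanted material. Protocol 6.1 sets out to assess safety when the spacer is used, and Protocol 5 describes the 6-month visit as the end point for assessing device safety. Protocol 6.4.9 lets RT start at any time up to 28 days after administration, so a reaction to the hydrogel has time to appear before RT begins.

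At stake is how the headline safety count reads. If a hydrogel reaction postponed RT and the CEC attributed it to the device alone, the endpoint could report zero although the investigational product had delayed treatment. A reader would have to reconstruct the link from the listing.

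**Working it through.** The plan gives no figure for this endpoint to reproduce: no hypothesis, power or target rate is set. The check is a comparison of texts, followed by a small illustration.

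**1. What enters the numerator.** Set the endpoint against the attribution classes:

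| CEC attribution of an event that delays RT | Counted in the endpoint as worded? |
|---|---|
| Procedure only | Yes |
| Procedure and device, if both are allowed | Yes |
| Device only | No |
| Radiotherapy or other | No |

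The third row is the gap. The second depends on a convention that neither document states. Protocol 9.1 defines an adverse device effect, but neither document defines a procedure-related event.

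**2. Where a device-only delay would be reported.** Under SAP 3.4.1 the event would appear in the tables by term, by relationship and by severity; in the device-related AE count; in the duodenal, SAE, SADE or UADE counts if it qualifies; and in the subject listing. The listing has fields for attribution, action taken and outcome, but none for RT delay. The only summary that uses RT delay is the endpoint itself, which has the procedure restriction.

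**3. Size for one event.** Inputs: n = 6 (Protocol 7.1, SAP 3.1.2), taken as the safety denominator of subjects with attempted administration (SAP 4.1.5). Exact 95% limits are shown for scale only, because the plan asks for none on this endpoint.

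- Not counted: 0/6 = 0%. Upper limit 1 − 0.025^(1/6) = 45.9%.
- Counted: 1/6 = 16.7%. Lower limit 1 − 0.975^(1/6) = 0.4%. The upper limit solves (1 − p)^6 + 6p(1 − p)^5 = 0.025, giving 64.1%.

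**4. Chance that the endpoint reads zero although a delay occurred.** The documents give neither the delay risk p nor the share s of delays adjudicated device-only, so both are assumed. With independent subjects, the chance is (1 − p(1 − s))^6 − (1 − p)^6.

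| Assumed p | At least one delay | s = 0 | s = 0.5 | s = 1 |
|---|---|---|---|---|
| 10% | 0.469 | 0 | 0.204 | 0.469 |
| 20% | 0.738 | 0 | 0.269 | 0.738 |
| 30% | 0.882 | 0 | 0.260 | 0.882 |

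For example, p = 0.10 and s = 0.5 give 0.95^6 − 0.90^6 = 0.735 − 0.531 = 0.204. The result depends almost wholly on s. If the CEC attributes every hydrogel reaction to the procedure as well, s = 0 and nothing is missed.

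**The case against.** The strongest reply is that exclusion is not certain. A reader might infer that any delay caused by the hydrogel must score zero. The documents do not support that: the classes are not said to be mutually exclusive, procedure-related is undefined, and the CEC could treat a reaction to freshly injected material as a consequence of its administration. This stands, and it limits the point to device-only attribution. It also means that the count rests on an unwritten convention.

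A reader might also infer that such an event would be hidden, or visible in just one device-related count. That is not so, as the reporting routes above show. Protocol 9.1 also includes, in its definition of an adverse event, consequences of a study-related delay in radiation, without separating device from procedure. With six subjects the listing will be read case by case. What remains missing is one summary that joins device attribution to RT delay.

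Third, nothing is decided on this percentage. There is no hypothesis (SAP 3.1.1), no interim analysis (SAP 5.2) and no success threshold. CEC review of serious events and the termination provisions are not limited to procedure-related events. A procedural focus also fits the purpose given in Protocol 7.1, so the narrow wording may be deliberate. This stands too, although neither document gives a reason for leaving out device-attributed delay.

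Finally, neither document says from what planned date a delay is measured, so a reaction within the 28-day window might not count as a delay under either wording. That is a separate gap.

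**Conclusion.** The point holds in a limited form. As worded, the only defined safety endpoint leaves out an RT delay that the CEC attributes to the device and not to the procedure, although the documents separate these attributions and name RT delay as a possible complication of TraceIT use. Each such subject is worth one sixth, or 16.7 percentage points, on a denominator of six. That size assumes that the case occurs and is adjudicated device-only; the documents allow this but do not say how likely it is.

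A reader might take this for a serious flaw in the safety evaluation. The documents do not support that reading: the endpoint is descriptive, the event is reported elsewhere, and no rule or planned interval depends on the rate. It is a cheap improvement, not a must-fix error.

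**What to change.** In the Protocol Summary, Protocol 6.1.1 and 7.7, and SAP 3.4 and 3.4.1:

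1. Define the endpoint as events adjudicated as related to the TraceIT device, the administration procedure, or both, that delay the start of RT.
2. Report the number and percentage of subjects in total and split by CEC class (procedure only, device only, both).
3. State that an event may carry both attributions.

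The CEC classes need not change. The cost is a few words in two documents and one extra table row or split. No data are needed beyond the attribution and the finding of delay that adjudication already requires. The downside for the sponsor is a possibly less favourable rate.
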